## 10.4 Prior and Concomitant Medications

Prior medications are medications with a start date prior to first date of vaccination. Concomitant medications are those ongoing at or starting on or after the start of vaccination.

## 10.5 Adverse Events (AEs)

An AE is any untoward medical occurrence in a subject or clinical investigation subject administered a pharmaceutical product and which does not necessarily have a causal relationship with this vaccination.

For outputs presenting occurrence of AEs for a defined period after a dose, the following distinctions are made if not otherwise stated; by any dose, dose 1, dose 2 and booster at day 57 and day 180. Any dose is defined as a subject who received at least one dose of either CVnCoV or active control.

### 10.5.1 Treatment Emergent Adverse Events (TEAE)

A TEAE is any AE that first occurs or increases in severity or relationship to trial vaccine after the first dose of vaccine. AEs which change in severity or relationship to trial vaccine are assigned a new start date and captured as a new record in the CRF. Hence, an AE is defined as TEAEs if the start date/time is after the date/time of first vaccination. Imputed AE start date/time as defined in Section 10.3 will be considered when assessing if an AE is treatment emergent. If the AE start date is still missing after applying imputation rules (i.e. missing year), the AE will be considered treatment emergent.

All solicited AEs are considered treatment emergent, even in the case that (partially) missing or conflicting date/time information is recorded or imputed.

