Moderate (Grade 2): An event that causes sufficient discomfort to interfere with normal everyday activities.

Severe (Grade 3): An event that prevents normal everyday activities. An AE that is assessed as severe should not be confused with an SAE. Severe is a category utilized for rating the intensity of an event; and both AEs and SAEs can be assessed as severe.

An event is defined as 'serious' when it meets at least 1 of the predefined outcomes as described in the definition of an SAE, not when it is rated as severe.

Assessment of Causality

- The Investigator is obligated to assess the relationship between the trial vaccine and each occurrence of each AE/SAE. Causality will be determined as:
 - **Related:** There is a reasonable causal relationship between the trial vaccine and the AE.
 - **Unrelated:** There is no reasonable causal relationship between the trial vaccine and the AE.
- A "reasonable possibility" of a relationship conveys that there are facts, evidence, and/or arguments to suggest a causal relationship, rather than a relationship cannot be ruled out.
- The Investigator will use clinical judgment to determine the relationship. Alternative causes, such as underlying disease(s), concomitant therapy or vaccination, and other risk factors, as well as the temporal relationship of the event to the trial vaccine administration will be considered and investigated.
- The Investigator will also consult the Investigator's Brochure for CVnCoV in his/her assessment.
- For each AE/SAE, the Investigator **must** document in the medical notes that he/she has reviewed the AE/SAE and has provided an assessment of causality.
- There may be situations in which an SAE has occurred and the Investigator has minimal information to include in the initial report to the CRO. However, **it is very important that the Investigator always makes an assessment of causality for every event before the initial transmission of the SAE data to the CRO.**
- The Investigator may change his/her opinion of causality in light of follow-up information and send a SAE follow-up report with the updated causality assessment.
- The causality assessment is one of the criteria used when determining regulatory reporting requirements.
- All local solicited symptoms are considered related to vaccination.

Recording of AEs and/or SAEs

AE and SAE Recording

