- The "**initial SAE report**" should be as complete as possible, including causality assessment, details of the current illness and (S)AE, the reason why the event was considered serious; date of onset and end date (if applicable); diagnostic procedures and treatment of the event; relevant medical history and concomitant medication and vaccinations; and action taken with the trial vaccine(s). The SAE report form **must be signed by the Investigator or his authorized designee(s)**.
- Investigator must inform the CRO about AESIs and cases of overdose by applying the same timelines and rules of SAE reporting.

Determination of Expectedness, Reference Safety Information

• Expectedness will be determined by the CRO according to the designated Reference Safety Information provided in the current Investigator's Brochure. Any updates or substantial amendments will be considered accordingly.
Observation Period

• For the purpose of this trial, the period of observation for collection of AEs required to be reported in the eCRF extends from the time the subject gives informed consent until the end of the trial, for the period described in Section 9.1.1.• All AEs that occur in the course of the clinical trial regardless of the causal relationship should be monitored and followed up until the outcome is known or it is evident that no further information can be obtained.• There must be documented reasonable attempts to obtain follow-up information and outcome.• It is the responsibility of the Investigator to ensure that any necessary additional therapeutic measures and follow-up procedures are performed.
Post-Trial Events

• If the Investigator becomes aware of any SAE that occurred after the end of the trial but is considered to be caused by the trial vaccine(s), this must be reported to the CRO.• These SAEs will be processed by the CRO. Instructions for how to submit these SAEs will be provided in a handout in the Investigator Site File.

Reporting of Other Events

Reporting and Follow-up of Pregnancies

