### 10.5.3 Unsolicited Adverse Events

Unsolicited AEs occurring on the day of vaccination and the following 28 days will be collected. For unsolicited AEs occurring on the day of dose 2 and the booster dose the following rule will be used:

If the AE is occurring on the day of dose 2 but before vaccination the AE will be presented with AEs for dose 1, if the AE is occurring on day of dose 2 but on or after vaccination it will be presented with AEs for dose 2. If this rule cannot be applied (for example, if the start time of the AE is missing) but the AE occurred on the day of vaccination for dose 2 it will be presented with the AEs for dose 2. The same rule applies for any unsolicited AE occurring on the day of the booster dose.

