### 12.8.1 Analysis of Unsolicited and Solicited AEs

An overall summary of unsolicited AEs will be prepared for AEs occurring within 28 days after each dose, within 28 days after any dose, and all reported AEs (including those reported at more than 28 days after any dose), presenting the number and percentage of subjects with

---

- Unsolicited AEs
- related unsolicited AEs
- grade 3 (severe) unsolicited AEs
- grade 3 (severe) related unsolicited AEs
- SAEs (includes solicited AEs)
- related SAEs (includes solicited AEs)
- intercurrent medical conditions affecting immune response (includes solicited AEs)
- AESIs (includes solicited AEs)
- related AESIs (includes solicited AEs)
- medically attended AEs (includes solicited AEs)
- related medically attended AEs (includes solicited AEs)
- AEs leading to vaccine withdrawal (includes solicited AEs)
- AEs leading to withdrawal from trial (includes solicited AEs)

The overall summary will also be presented by sex (female/male) for any dose regardless of retrospective serology status at baseline.

The following summaries of AEs by SOC and PT will further be provided, separately for AEs occurring within the first 28 days after each vaccination, within the 28 days after any vaccination, and all reported AEs (including those reported at more than 28 days after any dose) if not otherwise stated:

- Occurrence of unsolicited AEs
- Occurrence of related unsolicited AEs
- Occurrence of unsolicited AEs by maximum severity (mild / moderate / severe)
- Occurrence of related unsolicited AEs by maximum severity (mild / moderate / severe)
- Occurrence of SAEs (includes solicited AEs)
- Occurrence of related SAEs (includes solicited AEs)
- Occurrence of SAEs by maximum severity (mild / moderate / severe) (includes solicited AEs)
- Occurrence of related SAEs by maximum severity (mild / moderate / severe) (includes solicited AEs)
- Occurrence of intercurrent medical conditions affecting immune response (includes solicited AEs)
- Occurrence of AESIs (includes solicited AEs)
- Occurrence of related AESIs (includes solicited AEs)
- Occurrence of medically attended AEs (includes solicited AEs)
- Occurrence of related medically attended AEs (includes solicited AEs)
- Occurrence of AEs leading to vaccine withdrawal (includes solicited AEs)
- Occurrence of AEs leading to withdrawal from trial (includes solicited AEs)
- Occurrence of AEs related to SMQs as defined in Section 10.5.9 (includes solicited AEs)

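### SAP 10.5.1 gives an AE that only improves a new start date, so an unsolicited AE from dose 1 can put the subject in the dose 2 or booster tables

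*SAP*

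**What the plan says.** SAP 10.5.1 contains three consecutive statements:

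- The definition: "A TEAE is any AE that first occurs or increases in severity or relationship to trial vaccine after the first dose of vaccine".
- The recording rule: "AEs which change in severity or relationship to trial vaccine are assigned a new start date and captured as a new record".
- The operating rule: "Hence, an AE is defined as TEAEs if the start date/time is after the date/time of first vaccination".

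SAP 10.5.3 assigns unsolicited AEs to a dose by timing: "if the AE is occurring on day of dose 2 but on or after vaccination it will be presented with AEs for dose 2". The same rule applies to the booster. SAP 12.8.1 then builds the tables by window: "An overall summary of unsolicited AEs will be prepared for AEs occurring within 28 days after each dose". It also has tables for 28 days after any dose and for all reported AEs. These tables, like the estimands in SAP 9.4, give numbers and percentages of subjects. Under SAP 12.8, the denominator after dose 2 or the booster is the subjects who received that dose.

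Protocol Appendix 10 places AE collection in the eCRF over a period that "extends from the time the subject gives informed consent until the end of the trial", subject to the periods in Protocol 9.1.1. On causality it says "The Investigator may change his/her opinion of causality in light of follow-up information", and handles this by an SAE follow-up report. Its follow-up rules send new or updated information to the eCRF entry first completed.

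**The concern.** The definition speaks of an increase and the recording rule of any change. The operating rule then draws its conclusion from the recording rule. A start-date test agrees with the definition only if new records arise solely from increases. As written, an improvement passes the test.

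Unsolicited AEs after Day 1 and Day 29, with their intensity and relationship, are a primary endpoint (Protocol 4.2.1). The per-dose tables are where a reader looks for a difference in tolerability between dose 1, dose 2 and the booster. A resolving dose 1 event that reappears under dose 2 blurs that comparison. A related record left standing after the Investigator has withdrawn the attribution would overstate related events.

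**Working it through.** The documents give no figure that depends on this rule, so there is none to reproduce. The check applies the SAP's date logic to worked cases and then sizes one misplaced subject.

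**Inputs.** Dose 1 is on Day 1 and dose 2 on Day 29 (Protocol Table 2). The window is the vaccination day plus 28 days, so Days 1 to 29 for dose 1 and Days 29 to 57 for dose 2. A record on Day 29 at or after the injection goes to dose 2.

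**Cases under the SAP as written.**

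| Unsolicited AE | Records | Result |
|---|---|---|
| Grade 2 from Day 20, Grade 1 from Day 31 | Day 20, Day 31 | Dose 1 and dose 2 |
| Grade 2 from Day 20, Grade 1 from Day 25 | Day 20, Day 25 | Dose 1 only; no extra subject |
| Onset Day -5, improves on Day 4 | Day -5, Day 4 | Second record is treatment-emergent and in the dose 1 window |
| Onset Day 10, causality revised from related to unrelated on Day 35 | Day 10, and a second record whose date the SAP does not specify | If dated Day 35: dose 1 (related) and dose 2 (unrelated). If dated Day 10: both under dose 1, and the related record still stands |

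In the first and third cases nothing first occurred or increased at the second record, so the definition is not met although the operating rule is.

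**Is there a repair elsewhere in the SAP?** Section 10.5.2 collapses overlapping solicited diary records on the same day. Section 10.5.7 deals with events that run past the next dose, but only for the duration of solicited AEs. Neither reaches unsolicited AEs. No rule links a split record to its predecessor or tests the direction of the change.

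**Which AEs can be affected.** Grade 0 means no AE (Protocol Appendix 10), so a Grade 1 event can only resolve. A step down needs Grade 2 or 3.

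**Size per affected subject.** One subject with no genuine AE of that kind after dose 2 adds 100/N percentage points to that row.

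- 12 µg, one age group: N = 90 + 200 = 290 (SAP 12.0 combines initial phase and expansion); 100/290 = 0.34 points.
- Group 2: N = 12; 100/12 = 8.3 points.

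These take N as the planned number and assume that every subject received dose 2.

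**After the correction.** The Day 20 AE counts once, under dose 1. The Day -5 AE is not treatment-emergent. The Day 10 AE counts once, under dose 1, with the latest causality.

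**The case against.** The case on the other side removes several stronger readings that a reader might infer.

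- *All AE counts are inflated.* The tables count subjects. An AE that began within 28 days of dose 1 already has its subject in the any-dose rows, and a split record adds nothing to a dose 2 row if the subject has another qualifying AE there.
- *Solicited reactogenicity is affected.* On Days 1 to 8 solicited AEs follow diary days, relatedness is assessed once overall, and tables use the maximum grade (SAP 10.5.2, 12.8.2). Those tables are untouched.
- *The treatment-emergent flag drives the tables.* No table listed in SAP 12.8 is defined by it. The effect comes through start date and the 28-day window.
- *A sizeable share of dose 1 AEs is counted twice.* With onset uniform over 28 days and exponential duration of mean m days, the share still ongoing at dose 2 is (m/28)(1 − exp(−28/m)): 10.7%, 24.5% or 43.2% for m = 3, 7 or 14. These inputs are not in the documents. Being ongoing is not the same as stepping down a grade after dose 2, Grade 1 events cannot step down, and a share of events is not the bias in a subject-level table.
- *Causality corrections certainly create second events, and related SAEs vanish from view.* The SAP does not say which date a revision receives, and the protocol's follow-up rule points to updating the existing entry. SAEs are a primary endpoint throughout the trial. They also appear in the all-reported tables and a by-subject listing, so re-dating does not hide them.

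The pre-vaccination case is also narrowed. Protocol 6.3 provides for delaying vaccination for a Grade 2 or higher infection or acute disease in the preceding three days.

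What remains is the mismatch between increase and change, the absence of any linking rule for unsolicited AEs, and the conflict with the protocol on causality updates.

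**Conclusion.** The point holds within these limits. Followed literally, SAP 10.5.1 with 10.5.3 and 12.8.1 places a subject whose Grade 2 or 3 unsolicited AE merely improved on or after a later dose in that dose's 28-day tables. It also classes a pre-vaccination AE that improved after dose 1 as treatment-emergent, and that AE can enter the dose 1 tables.

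The error is at most 0.34 points per affected subject at N = 290 and 8.3 points at N = 12, and nil where the subject has a genuine AE of that kind after the dose. The number of such subjects cannot be derived from the documents. The analysis is descriptive, so no test result is at stake, only the accuracy of per-dose primary safety percentages.

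On causality, the conclusion is conditional. The SAP and Protocol Appendix 10 disagree on whether a revision opens a new record. If both records are kept, an AE or SAE revised from related to unrelated stays in the related tables.

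**What to change.** In SAP 10.5.1:

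1. Link contiguous records of the same event, by an eCRF link if one exists and otherwise by subject, term and adjoining dates.
2. Let only a grade higher than that of the preceding record create a new onset for treatment-emergent status and dose attribution. A record with a lower grade keeps the original start date.
3. Reconcile the section with the follow-up rule in Protocol Appendix 10, so that a causality revision updates the existing record. The related tables then use the Investigator's latest assessment with the original onset date. An increase in relationship would then no longer be a criterion for emergence, and the definition should say so.

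The cost is SAP wording and one derived linking variable. Whether eCRF version 5.0 already holds a link is not known from the documents; without one, matching on term and dates needs some data review. SAP 6.0 allows an amended SAP to be approved up to final database lock.

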4.2.1 Primary

- The frequencies, intensities, and duration of solicited local AEs on Day 1 and Day 29 and the following 7 days by dose and group.
- The frequencies, intensities, duration, and relationship to trial vaccination of solicited systemic AEs on Day 1 and Day 29 and the following 7 days by dose and group.
- The occurrence, intensities and relationship to trial vaccination of unsolicited AEs on Day 1 and Day 29 and the following 28 days by dose and group.
- The occurrence and relationship to trial vaccination of SAEs and AESIs throughout the trial.

On Day 29 and Day 43:

- The proportion of subjects seroconverting for SARS-CoV-2 spike protein antibodies, as measured by ELISA.

- Individual SARS-CoV-2 spike protein-specific antibody levels in serum, as measured by ELISA.
- Geometric mean titers (GMTs) of serum SARS-CoV-2 spike protein antibodies, as measured by ELISA.
- The proportion of subjects seroconverting for SARS-CoV-2 neutralizing antibodies, as measured by an activity assay.
- Individual SARS-CoV-2 neutralizing antibody levels in serum.
- GMTs of serum SARS-CoV-2 neutralizing antibodies, as measured by an activity assay.

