## 10.3 Missing Data

Analysis of vaccination data will be done on a valid case basis, i.e., for missing observations, no imputation for missing data, such as last observation carried forward, will be applied. For nCoV spike protein antibodies and Virus Neutralization, concentration values marked as below the cut point (CP) will be set to 0.5\*CP.

No imputation of missing values will be done for any analysis (except the imputation for missing partial dates of AEs and concomitant medication). Reasons for discontinuation from the trial or trial vaccination will be listed and summarized.

Currently no replacement of drop-out subjects is foreseen.

For unsolicited AEs, solicited AEs occurring after Day 8 and concomitant medications, some missing or partially missing variables will be imputed as follows:

For AE or concomitant medication start date:

- If start date year value is missing, the date uncertainty is too high to impute a rational date. Therefore, if year value is missing, the imputed AE start date is set to missing.
- If start date year value is before the vaccination start date year value, started before the vaccination. Therefore:
  - If month is missing, the imputed start date is set to the mid-year point (i.e., 01JULYYYY).
  - If month is not missing, the imputed start date is set to the mid-month point (i.e., 15MONYYYY).
- If start date year value is equal to the vaccination start date year value, the start date month needs to be compared against the vaccination start date month, to determine the imputation rule to apply. Therefore:
  - If month is missing, the imputed month and imputed day is the same as start of vaccination
  - If month is lower than vaccination start date month and start date day is missing, the imputed start date is set to the mid-month point (i.e. 15MONYYYY).
  - If month is equal to the vaccination start date and start date day is missing, the start day will be set to the start day of vaccination.
  - If month is greater than the vaccination start date month and start date day is missing, the imputed start date is set to the beginning of the month (i.e., 01MONYYYY).
- If start date year value is greater than the vaccination start date year value, started after vaccination. Therefore,
  - If month is missing, the imputed start date is set to the year start point (i.e., 01JANYYYY).

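### SAP 10.5.1 requires an AE to start after first vaccination, but 10.3 imputes two kinds of partial start date to the vaccination date itself, so those unsolicited AEs are classed as not treatment-emergent

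*SAP*

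**What the plan says.** SAP 10.5.1 gives the working definition: "an AE is defined as TEAEs if the start date/time is after the date/time of first vaccination". It adds that "Imputed AE start date/time as defined in Section 10.3 will be considered when assessing if an AE is treatment emergent". Two exceptions follow. An AE whose start is still missing after imputation, because the year is missing, is treated as emergent. All solicited AEs are emergent whatever their dates.

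SAP 10.3 introduces its imputation rules with "For unsolicited AEs, solicited AEs occurring after Day 8 and concomitant medications, some missing or partially missing variables will be imputed as follows". For a start in the same year as vaccination, two rules return the vaccination date:

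- Month missing: "If month is missing, the imputed month and imputed day is the same as start of vaccination".
- Month the same as the vaccination month, day missing: "the start day will be set to the start day of vaccination".

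The rules supply a date, never a time. They come from the SAP alone, because Protocol 10.3.6 has no rule for a start in the vaccination year.

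Neighbouring rules compare differently. SAP 10.4 counts a medication as concomitant if it is ongoing at, or begins on or after, the start of vaccination. SAP 10.5.3 says an AE occurring "on day of dose 2 but on or after vaccination it will be presented with AEs for dose 2". It also sends a same-day AE that cannot be ordered, for example because its time is missing, to dose 2, and it extends the rule to the booster. Dose 1 has no such sentence. The primary endpoint in Protocol 4.2.1 covers "unsolicited AEs on Day 1 and Day 29 and the following 28 days by dose and group".

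**The concern.** The imputation and the test that uses it work against each other. The SAP does not say why 10.3 chooses the vaccination date, but that choice, the missing-year rule and the same-day rule for later doses all lean towards counting an uncertain event as following vaccination. The strict comparison in 10.5.1 reverses this for the two same-year patterns. The outcome is also out of order: a record with no date information is emergent, while one known to fall in the month of vaccination is not. A drug and the AE it treats, with identical partial dates, would be concomitant and non-emergent respectively.

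Safety after one and two doses is a primary objective. Protocol Appendix 10 starts AE recording at informed consent, and Protocol section 9 allows eligibility procedures up to 21 days before vaccination, so AEs from before the injection may be in the database. SAP 10.5.1 is the only explicit rule that classifies an AE as arising before or after first vaccination. If it is used to select events, any misclassification of these records runs towards fewer events after vaccination.

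**Working it through.** There is no plan figure to reproduce. The check applies the SAP 10.3 start-date rules to each partial-date pattern and then applies the 10.5.1 test.

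**Inputs.** The rules are as set out above, reading the vaccination start date in 10.3 as the date of first vaccination. Assumed for illustration: first vaccination on 15 October 2020 at 10:00, repeated with 1 December 2020. The test was tried on dates alone, and on date/time with the unimputed time taken as 00:00.

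| AE start as recorded | Imputed start (vaccination 15 Oct 2020) | After? (10.5.1) | On or after, by date? |
|---|---|---|---|
| Year missing | none | Emergent by explicit rule | Emergent by explicit rule |
| Earlier year, month missing | 1 Jul 2019 | No | No |
| Earlier year, day missing (May) | 15 May 2019 | No | No |
| **Same year, month missing** | **15 Oct 2020** | **No** | **Yes** |
| Same year, earlier month, day missing | 15 Sep 2020 | No | No |
| **Same year and month, day missing** | **15 Oct 2020** | **No** | **Yes** |
| Same year, later month, day missing | 1 Nov 2020 | Yes | Yes |
| Later year, month missing | 1 Jan 2021 | Yes | Yes |
| Later year, day missing (Feb) | 1 Feb 2021 | Yes | Yes |

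**Results.**

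1. The two bold patterns fail the strict test on dates, because 15 October is not after 15 October. They fail on date/time, because 00:00 is not after 10:00. Copying the vaccination time as well gives a tie, which also fails.
2. Exactly two of the nine patterns change class under on or after by date. The other seven keep theirs.
3. The December date gives the same classes for every pattern it can produce. There is no later month in that year.
4. The one-word change is enough only when dates are compared. With the time set to 00:00, the imputed start is still earlier than a 10:00 injection, so a missing-time rule is also needed.
5. A complete Day 1 date without a time is a separate case. Nothing is imputed, and 10.5.1 compares date/time without saying what to do when the time is absent. The text does not settle the class.

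**The case against.** The strongest reply is that no specified output uses the flag. The estimand table in SAP 9.4 and the summaries in SAP 12.8 never mention treatment emergence. The unsolicited AE tables are defined as events within 28 days of each dose, within 28 days of any dose, and all reported AEs. SAP 10.5.3 counts the day of vaccination in the collection period, so an AE dated or imputed to Day 1 can still be tabulated. Protocol 9.1.1.2 limits eCRF entry to the reporting period, which narrows how many pre-injection AEs could be present, and Protocol 11.4 has missing data queried.

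All of this stands, and it limits the consequence. It does not remove the contradiction. Either 10.5.1 is applied and misclassifies the two patterns, or it has no stated use and the all-reported-AEs tables have no written exclusion of events before the injection. SAP 12.0 also puts derived variables into the listings, so the flag can appear there.

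A reader might go further and infer any of the following, which the documents do not support:

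- **Events are lost from the primary safety tables.** That needs a restriction to treatment-emergent AEs, and SAP 12.8 states none.
- **The dose 1 versus dose 2 comparison is distorted.** This needs the same restriction. In addition, an AE with only the year recorded could have begun after dose 2 and would still be imputed to first vaccination, so any loss would not fall on dose 1 alone. The same-day rule in 10.5.3 allocates an event between two doses, a choice that does not arise at dose 1.
- **Untimed Day 1 AEs are definitely excluded.** The text is silent on them.
- **The share of AEs lost can be estimated.** The documents give no counts of partial dates, so any percentage would rest on invented calendars and onset patterns.

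**Conclusion.** The contradiction is real and holds under every literal reading tested. Unsolicited AEs in the two same-year patterns are classed as not treatment-emergent, against the on-or-after comparison in SAP 10.4 and 10.5.3 and out of order with the missing-year rule. Day 1 AEs without a time are ambiguous. Solicited AEs are untouched.

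The severity is minor. The number of affected records is unknown, and an effect on a specified table is possible but not shown. For scale only: if a table were restricted to treatment-emergent AEs, and the affected event were the subject's only qualifying one, one subject would be 1/11 = 9.1 or 1/12 = 8.3 percentage points in a 6 µg group, and 1/60 = 1.7 points in the pooled controls (10 + 10 + 40 = 60). Neither condition is established.

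The conclusion assumes that the vaccination start date in 10.3 means first vaccination. That the imputation was meant to be conservative is inferred from the surrounding rules, not stated.

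**What to change.** In SAP 10.5.1:

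- Replace after by on or after.
- Add that an unsolicited AE whose recorded or imputed start date equals the date of first vaccination, and whose time is missing, is treatment-emergent and presented with dose 1, unless it is recorded as starting before the injection.

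In SAP 12.8, state which outputs, if any, use the flag.

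The cost is a few sentences of SAP text and one changed comparison in the derivation, with no new data. The downside is that a few Day 1 or same-month events that began before the injection may be counted. The SAP already accepts a similar trade-off for same-day AEs at dose 2 and the booster, and for AEs with no year.
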